### Study Interventions and Measures:

Contrast-enhanced ultrasound scan with a duration of approximately 15 minutes will be performed when a COVID-19 diagnosis has been made (or is highly suspected) according to established clinical procedures. One CEUS will be performed per patient, with up to 2 intravenous injections of the contrast agent. The dosing plan will be weight-adjusted, based on a dose of 0.03 mL/kg (with a maximum dose of 2.4 mL per injection). Organ perfusion will be evaluated in the heart, kidneys, and/or brain. Clinical outcomes during hospital stay will be collected for correlation to CEUS-based measures.

---

---

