**Figure 3.** CEUS of the kidneys. Shown are sagittal CEUS images of the kidneys, (A) demonstrating homogeneous perfusion of normal right kidney with high signal due to intravascular microbubbles and (B) demonstrating low signal regions (yellow arrows) consistent with ischemia.

**CEUS Quantification:** It should be noted that CEUS gives a wide range of quantifiable, continuous parameters reflective of tissue perfusion. Injection of contrast results in increased acoustic signal quantifiable as signal intensity in decibels (dB). Spatiotemporal changes in signal intensity are then measured to reflect tissue perfusion, flow rate, blood volume, and many other parameters that can be derived from the *time intensity curve (TIC)* analysis. In TIC analysis, signal intensity in a given region of interest is plotted over time and parameters are extracted from the curve (for e.g. time to peak or TTP, wash-in area under the curve or WiAUC, rise time or RT, wash-in rate or WiR, wash-in perfusion index or WiPi). This is a well-accepted conventional approach to CEUS quantification previously used by the PI in the report of the first clinical guidelines for application of brain CEUS in infants (29), quantitative detection of hypoxic ischemic injury using brain CEUS (30), and quantification of tumor microvessel density (35). More advanced analysis involves the particle tracking method, in which individual intravascular microbubbles are tracked across thousands of ultrasound frames to quantify microbubble velocity, spatial distribution, trajectory (and other sophisticated parameters such as shear stress, acceleration-deceleration, etc.) (36). The conventional time intensity curve and particle tracking method combined would yield more than >30 continuous CEUS microvascular perfusion parameters that can each, or in combination, be correlated to clinical outcomes in this proposal.

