## **3 INVESTIGATIONAL PLAN**

### **3.1 General Schema of Study Design**

This is a pilot study in which 30 subjects with confirmed or probable COVID-19 will undergo CEUS of heart, kidneys and/or brain.

The dosing plan will be weight-adjusted, based on a dose of 0.03 mL/kg. Each patient will receive up to two contrast injections as per the product label/FDA approved guidelines, with a maximum dose of 2.4 mL per injection. Examinations (heart, kidneys, and/or brain) will be made at the same time, as soon as the first product intravenous injection takes place. The examination will last approximately 15 minutes but no more than one hour.

As exploratory analysis, CEUS findings on these patients will be correlated to clinical outcomes (death, mechanical ventilation, heart attack, stroke, and renal failure).

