### 5.2 Secondary Endpoints

1. Evaluate heart, kidneys and/or brain perfusion using time to peak (TTP) and wash-in area under the curve (WiAUC).
2. Death within 28 days of imaging or mechanical ventilation within 14 days of imaging as reported in the medical chart.
3. Myocardial infarction, stroke, or renal failure as reported in the medical chart.

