### 5.3 Sample Size and Statistical Analysis Plan

We will enroll 30 subjects (15 male/15 female) in this pilot study. As part of clinical care, CHOP Radiology also performs approximately 4-5 contrast-enhanced ultrasound cases in a given day, which is higher in volume than any other children's hospital in the country.

---

A sample size of 30 should provide reasonable estimates of the perfusion metrics. For example, a sample size of 30 participants produces a two-sided 95% CI with a width equal to 0.3 when the estimated proportion is as small as 0.3 (95% CI=0.1, 0.5). Also, a two-sided 95% CI with a width equal 0.6 when the estimate of Pearson's product-moment correlation is 0.4 (95% CI= 0.05, 0.7).

Based on microangiopathy/ischemia observed in COVID-19 patients (9-11), we expect our cohort to display delayed perfusion, hypoperfusion or no perfusion of the myocardium, kidneys, and/or brain. Results of the myocardial, renal and brain perfusion will be assessed by two experienced researchers in the field of CEUS and report it qualitatively as either normal or abnormal. In case of diagnosis disagreement between the two raters, a third experienced researcher will confirm the correct diagnosis. Hence, the proportion and frequency of myocardial, renal, and/or brain perfusion abnormalities will be documented. As additional primary analysis, we will also assess quantitative CEUS and derive time-to-peak (TTP) and wash-in area under the curve (WiAUC).

Demographic characteristics and descriptive statistics (such as measures of frequency, central tendency, dispersion, and position) will be summarized for the sample and by male and female sex. The percentage of COVID-19 patients with an abnormal clinical exam will be computed. Time intensity curve analysis will provide further details on the nature of perfusion abnormalities. The following presents the variable names, output, and the reported statistics for the primary and secondary aims.

	Measured Variables	Output and statistics
Primary Analysis	Perfusion defect (hypo- or absent perfusion)	Proportion of COVID-19 patients with perfusion defect
Primary Analysis	Perfusion quantified using time-to-peak (TTP) and wash-in area under the curve (WiAUC) from the time-intensity curve of contrast signal	Summary statistics for TTP and WiAUC, for e.g. mean, standard deviation, 95% CI
Secondary Analysis	Clinical outcomes from chart review etc.	Correlation of CEUS metrics to clinical outcomes

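### Does Section 5.3 need a rule that reduces TTP and WiAUC to one value per patient before their mean and 95% CI can be trusted?

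*Combined protocol and SAP*

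**What the plan says.** Section 5.3 lists, for the two time-intensity-curve parameters, "Summary statistics for TTP and WiAUC, for e.g. mean, standard deviation, 95% CI", and for the secondary aim a correlation of CEUS metrics with clinical outcomes. The background in Section 1.1 gives the level of measurement: "In TIC analysis, signal intensity in a given region of interest is plotted over time and parameters are extracted from the curve". Section 3.1 states that "30 subjects with confirmed or probable COVID-19 will undergo CEUS of heart, kidneys and/or brain", and the abstract adds: "One CEUS will be performed per patient, with up to 2 intravenous injections of the contrast agent". Section 4 limits brain imaging to patients with new-onset neurological symptoms.

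On size, Section 5.3 asserts: "A sample size of 30 should provide reasonable estimates of the perfusion metrics". It supports this with two examples at 30 participants: a proportion of 0.3 (interval 0.1 to 0.5, width 0.3) and a Pearson correlation of 0.4 (interval 0.05 to 0.7, width 0.6). The table in Section 5.3 names the patient as the unit for the perfusion-defect proportion. The TTP and WiAUC row names no unit. Section 5.2 lists TTP and WiAUC as a secondary endpoint, while Section 5.3 calls them an additional primary analysis.

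**The concern.** A patient with both kidneys imaged after two injections could supply four renal curves, and heart or brain curves as well. The plan does not say which curve counts, how several are combined, or whether results are per organ or pooled. Three values of n are therefore conceivable for the same mean: curves, patients, or patients with that organ imaged.

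Curves from one patient are correlated. If each entered as a separate observation, the standard error would be too small and the interval too narrow. Section 1.1 says the descriptive statistics and confidence intervals from this pilot are meant to inform a future trial, so a falsely tight interval would be passed on. Separately, the two precision examples use all 30 participants. An organ-level result may rest on fewer, and no precision is given for a mean, which is the statistic planned for TTP and WiAUC.

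**Working it through.** **1. The plan's own figures, n = 30.**
- Proportion 0.3, Wald: 0.3 ± 1.96 × √(0.3 × 0.7/30) = 0.136 to 0.464, width 0.328. Exact interval for 9/30: 0.147 to 0.494, width 0.347. Both agree with the printed 0.1, 0.5 and 0.3 at one decimal.
- Correlation 0.4, Fisher z: tanh(atanh 0.4 ± 1.96/√27) = 0.046 to 0.665, width 0.618. This agrees with the printed 0.05, 0.7 and 0.6.

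Both examples reproduce with one observation per participant.

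**2. What would happen if curves were counted as observations.** Assumed, because the documents give neither: k = 2 or 4 values per patient, and within-patient correlation ρ from 0.3 to 0.9. The variance of the mean is inflated by 1 + (k − 1)ρ, so the coverage of a nominal 95% interval is 2Φ(1.96/√(1 + (k − 1)ρ)) − 1.

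| k | ρ | Inflation | Coverage, formula | Coverage, simulated |
|---|---|---|---|---|
| 2 | 0.3 | 1.3 | 0.914 | 0.915 |
| 2 | 0.9 | 1.9 | 0.845 | 0.842 |
| 4 | 0.3 | 1.9 | 0.845 | 0.848 |
| 4 | 0.9 | 3.7 | 0.692 | 0.686 |

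The simulation used 30 patients and 100,000 runs. An interval on one mean per patient covered 0.950 to 0.952 in every case.

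**3. Widths on a common scale (SD of a single curve).**
- Naive interval on all curves, t/√(30k): 0.258 for k = 2 and 0.181 for k = 4.
- Correct interval on patient means, (t₂₉/√30) × √((1 + (k − 1)ρ)/k), with t₂₉/√30 = 0.373:
  - k = 2: 0.373 × √0.65 = 0.30 to 0.373 × √0.95 = 0.36.
  - k = 4: 0.373 × √0.475 = 0.26 to 0.373 × √0.925 = 0.36.

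The figure 0.373 itself applies when each patient supplies a single curve. Setting it against the naive widths overstates the loss whenever the alternative is a patient mean.

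**4. Effect on the SD, which a future sample-size calculation needs.** The expected pooled variance is σ² × (30k − [1 + (k − 1)ρ])/(30k − 1). For k = 2, ρ = 0.3 this is 58.7/59 = 0.995. For k = 4, ρ = 0.9 it is 116.3/119 = 0.977. On the SD scale (square roots 0.997 and 0.989) the shortfall is about 0.3% to 1.1%. With equal numbers of curves per patient the mean does not change.

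**5. Organ-level n.** At an assumed 20 patients with a given organ imaged, r = 0.4 has a Fisher interval of −0.05 to 0.72, and the mean has a half-width of 0.47 SD. These intervals are wider but valid.

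**6. What the text points to.** Section 5.3 counts participants in its precision statement and patients in its primary proportion, and it names myocardial, renal and brain perfusion individually. The clinical outcomes in Section 5.2 occur once per patient, so a correlation with them calls for one CEUS value per patient. No section mentions pooling curves or organs.

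**The case for a change.** The strongest case for a change is that the plan permits both a valid and an invalid analysis, that the intervals are a stated product of the pilot, and that a sentence of text would close the gap without touching the sample size, the imaging or the data collection. It is true that no section gives the combining rule. It is also true that the precision examples carry over to an organ only if all 30 patients have it imaged; for brain that would require new neurological symptoms in every patient.

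What does not stand is the step from silence to harm. Undercoverage arises only under an analysis that no section describes, and its size rests entirely on assumed values of k and ρ. The case of four values is the least supported: the second injection is optional, and Section 3.1 has the organs examined together from the first injection. Nor would a short rule settle the measurement question. Averaging over regions can dilute a focal defect, a single region discards data, and either choice still leaves the regions themselves to be defined by the imaging team. The mismatch of label between Sections 5.2 and 5.3 is clerical; with no hypothesis test and no multiplicity control, it changes no result.

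**Conclusion.** The gap is real but minor, and it is not a sample-size error. Both printed intervals are right at 30 participants, and the patient-level proportion in Section 5.1 is untouched. The natural reading, one value per patient per organ with that organ's n, gives correct coverage. Only if curves were treated as independent would coverage fall to about 91% to 69%, with half-widths of 0.26 or 0.18 SD against a correct 0.30–0.36 or 0.26–0.36 SD (assuming k = 2 or 4 and ρ = 0.3 to 0.9).

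The conclusion assumes that the analyst respects the patient as the unit and reports n with each organ's summary, which is ordinary practice for descriptive imaging data. All CEUS images are kept (Section 4.4.2), so the choice of region and injection can be made at the analysis stage without loss of data. The correlations with outcome are described as exploratory in Section 3.1. No change to the plan is needed.

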## 5 STATISTICAL CONSIDERATIONS

### 5.1 Primary Endpoint

1. Estimate the proportion of patients with normal perfusion versus area(s) of hypoperfusion in heart, kidneys and/or brain.

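### Section 5.3 gives no rule for time-to-peak where no wash-in peak exists, so its mean and its correlation with outcome are likely to miss the most severely affected regions or organs

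*Combined protocol and SAP*

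**What the plan says.** The sample-size and analysis text in section 5.3 states that "we expect our cohort to display delayed perfusion, hypoperfusion or no perfusion of the myocardium, kidneys, and/or brain". The first Primary Analysis row of its table defines the event as "Perfusion defect (hypo- or absent perfusion"), so an organ with no perfusion counts as a defect. The second Primary Analysis row covers TTP and WiAUC, with the output "Summary statistics for TTP and WiAUC, for e.g. mean, standard deviation, 95% CI". The Secondary Analysis row correlates CEUS metrics with clinical outcomes without naming a coefficient. The only coefficient named in the section is Pearson's, in the precision example.

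The CEUS Quantification paragraph of section 1.1 explains where TTP comes from: "signal intensity in a given region of interest is plotted over time and parameters are extracted from the curve". Section 5.1 words the primary endpoint by area: "Estimate the proportion of patients with normal perfusion versus area(s) of hypoperfusion in heart, kidneys and/or brain".

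No section says what TTP is when the curve has no peak. The documents give no exclusion, censoring, assigned value, rank or missing-data rule. They also do not say where the region of interest is placed, how long the curve is recorded, or how several organs in one child are combined.

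**The concern.** TTP is the time at which a curve reaches its maximum. If no contrast arrives, the curve is flat and there is no such time. A peak that falls after the end of the recording is lost in the same way. The plan therefore predicts a state in which one of its two named quantitative metrics cannot be measured, and that state is the extreme of what TTP is meant to capture.

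Two things can happen in practice. The value is left blank and the region leaves the mean, the SD and the correlation, or software returns a time picked from noise. Neither is a valid measurement. With blanks, absent perfusion counts in the proportion but is missing from TTP, and the loss is tied to severity. Medians, which section 1.1 also lists, do not help if they are taken over the remaining curves only.

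Section 1.1 says these descriptive statistics are needed to design a future trial. A TTP mean pulled towards normal and an SD that is too small would carry over into that design.

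**Working it through.** **Inputs from the documents (section 5.3).** n = 30; two-sided 95% intervals; example proportion 0.3; example Pearson r = 0.4.

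**Assumed inputs.** The share of regions without a peak is not in the documents, so I take k = 1, 3 or 6 of 30, with one TTP per child. Severity s is standard normal. TTP has correlation a with s (a = 1.0, 0.7, 0.5). Outcome has correlation b = 0.4/a with s, so the full-sample TTP-outcome correlation is 0.40. The most severe k/30 are removed.

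**Step 1: the plan's own figures.**
- Proportion (Wald): 0.3 ± 1.96 × √(0.3 × 0.7/30) = 0.3 ± 0.164, or 0.136 to 0.464, width 0.328. The plan prints "two-sided 95% CI with a width equal to 0.3 when the estimated proportion is as small as 0.3 (95% CI=0.1, 0.5").
- Correlation (Fisher z): tanh(atanh 0.4 ± 1.96/√27) = 0.046 to 0.665, width 0.618. The plan prints "a width equal 0.6 when the estimate of Pearson's product-moment correlation is 0.4 (95% CI= 0.05, 0.7").

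Both reproduce after rounding. They are not in error; they assume that all 30 contribute.

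**Step 2: smaller n alone, observed r kept at 0.4.** n = 27 gives 0.024 to 0.677; n = 24 gives -0.004 to 0.692.

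**Step 3: selective loss.** Let c = Φ⁻¹(1 − k/30), λ = φ(c)/(1 − k/30) and v = 1 − cλ − λ². Then
- shift in mean TTP = −aλ, in SD units;
- r after loss = 0.4v / √{[1 − a²(1 − v)][1 − b²(1 − v)]}.

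For k = 3: c = 1.282, λ = 0.1755/0.9 = 0.195, v = 1 − 0.250 − 0.038 = 0.712. With a = 1 the shift is −0.195 SD and r = 0.285/√(0.712 × 0.954) = 0.346. Simulation of the same model (2 million draws) gives:

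| Lost of 30 | a | Shift in mean TTP (SD) | SD after loss | r | 95% CI at that r, n = 30 − k |
|---|---|---|---|---|---|
| 1 | 1.0 | -0.076 | 0.923 | 0.374 | 0.009 to 0.651 |
| 1 | 0.7 | -0.053 | 0.963 | 0.364 | -0.003 to 0.644 |
| 1 | 0.5 | -0.038 | 0.981 | 0.365 | -0.002 to 0.645 |
| 3 | 1.0 | -0.194 | 0.843 | 0.346 | -0.039 to 0.642 |
| 3 | 0.7 | -0.135 | 0.927 | 0.324 | -0.064 to 0.627 |
| 3 | 0.5 | -0.097 | 0.963 | 0.327 | -0.061 to 0.629 |
| 6 | 1.0 | -0.348 | 0.763 | 0.317 | -0.099 to 0.639 |
| 6 | 0.7 | -0.243 | 0.892 | 0.282 | -0.137 to 0.615 |
| 6 | 0.5 | -0.174 | 0.946 | 0.287 | -0.131 to 0.619 |

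**Step 4: scale.** The standard error of a mean at n = 30 is 1/√30 = 0.18 SD. Losing one case moves the mean by less than half of that (0.076/0.183 = 0.42). Losing six moves it by about one to two standard errors (0.174/0.183 = 0.95; 0.348/0.183 = 1.9).

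**The case against.** A reader might infer that the worst-affected children drop out. The documents do not support that. Nothing in them excludes anyone, and the loss is by region or organ. Section 5.1 speaks of areas, and section 1.1 mentions focal as well as diffuse infarct and shows low-signal regions within one kidney. A child with a focal defect, or with another perfused organ, may still have a TTP. A child is lost only if every measured region lacks a peak, and the unstated region-of-interest rule decides that.

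A reader might also infer that the whole quantitative row omits the sickest. That fails for WiAUC, which is near zero when no contrast arrives. Whether absent enhancement tracks clinical severity is itself part of what the study explores.

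The illustration has limits too. The loss rate has no source in the documents. The listed outcomes are mostly binary, whereas the model is bivariate normal. Organs are imaged according to symptoms (section 4), so the number per organ will often be below 30. The correlations are exploratory (sections 1.1, 3.1 and 4) and no test is planned, so an interval that reaches zero is a loss of precision and not a failed test.

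Finally, a mean among enhancing regions is a legitimate conditional quantity. The plan introduces its statistics as examples, and section 5.2 lists TTP as a secondary endpoint although section 5.3 calls it an additional primary analysis.

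All of this stands, and it limits the size and reach of the point. It does not supply the missing rule. A conditional mean has to be labelled as one, and a median of the surviving curves has the same gap.

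**Conclusion.** The point holds for TTP at region or organ level. Section 5.3 foresees absent perfusion, counts it as a defect, and plans a TTP mean and a correlation with no rule for a curve without a peak. If such values are left out, mean TTP leans towards normal and the correlation with outcome probably weakens.

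Under the assumed model, losing 1 to 6 of 30 shortens mean TTP by about 0.04 to 0.35 SD and lowers a true r of 0.40 to about 0.37 to 0.28. At one case the bias is small. These figures illustrate the mechanism; they do not predict this study's results, because the documents give neither the share affected nor the link between TTP and severity.

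Three stronger readings are not supported: that whole children necessarily drop out, that WiAUC is affected in the same way, and that the plan's stated confidence intervals are wrong.

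The rule should be fixed before images are read, since otherwise it would be chosen after the results are seen.

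**What to change.** In section 5.3 and its table, for each organ separately:

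1. Report TTP as median and quartiles with a confidence interval for the median.
2. Rank regions with a technically adequate scan but no enhancement as the longest TTP, or treat them as censored at the end of the recording. Treat a peak beyond the recording as longer than the recording. State the recording length.
3. Keep non-diagnostic scans apart as missing. Scan quality is already listed among the evaluations in the synopsis.
4. Keep WiAUC in with its measured near-zero value.
5. Use rank-based association: Spearman or Kendall, or a rank comparison between groups for a binary outcome.
6. State where the region of interest is placed.
7. Report the number of organs with and without a measurable peak, and label any mean TTP as *among regions with enhancement*.

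No extra children or scans are needed. The cost is SAP wording plus a decision on region-of-interest placement and recording length. The statistical downside is that medians and ranks are slightly less efficient than means and Pearson's r when every organ enhances.

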## 6 STUDY DRUG

### 6.1 Description

Lumason™ is currently FDA approved for use in the evaluation of heart and liver in the pediatric and adult population. Recommended intravenous dose for Lumason™ is weight-based, 0.03mL/kg as an intravenous injection, up to a maximum of 2.4mL per injection. The dosing plan will be weight adjusted, based on a dose of 0.03 mL/kg. Subjects will be monitored for potential side effects for 60 minutes following the final study drug dose. It is currently used clinically at CHOP radiology department for routine diagnostic ultrasound studies.

### **6.1.1 Drug Handling and Accountability**

Lumason™, will be maintained as a separate supply from the Radiology Department for accountability. For each subject, the Lumason™ lot number, expiration date, number of vials used, disposition of unused Lumason™, and discard procedure, will be recorded as part of the study record.

## **7 SAFETY MANAGEMENT**

As is standard clinical practice at CHOP, we will follow all current safety standards for CEUS established by the FDA and ACR to provide adequate protection from potential hazards or injuries to subjects. To assure the safety of the participants, all subjects will be monitored for adverse events during the procedure by direct communication through an intercom system and by visual observance. Data will only be transferred between members of the study team, and no identifiable data will be shared with non-CHOP or CHOP individuals who are not on the study team.

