## 3.3 Study Population

### 3.3.1 Inclusion criteria

1. Patient (male/female) hospitalized at CHOP.
2. Patient 17 years of age or younger.
3. Diagnosis of COVID-19 or high clinical suspicion for COVID-19 despite negative tests (according to the definition of probable case by the ECDC).
4. Patient has evidence of cardiovascular compromise, myocardial injury, acute kidney injury, and/or new-onset neurological symptoms).
5. Parental/guardian permission (informed consent)

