### **7.3 Definition of an Adverse Event**

An adverse event is any untoward medical occurrence in a subject who has received an intervention (drug, biologic, or other intervention). The occurrence does not necessarily have to have a causal relationship with the treatment. An AE can therefore be any unfavorable or unintended sign (including an abnormal laboratory finding, for example), symptom, or disease temporally associated with the use of a medicinal product, whether or not considered related to the medicinal product.

All AEs (including serious AEs) will be noted in the study records and on the case report form with a full description including the nature, date and time of onset, determination of non-serious versus serious, intensity (mild, moderate, severe), duration, causality, and outcome of the event.

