#### **8.3.2 Risk Assessment**

The potential risks associated with contrast-enhanced ultrasonography have been extensively studied, and the risk associated with the technique is less than that of CT or MRI contrast agents. The risk of adverse events is the lowest of all contrast agents available, with CT contrast being the highest (0.6%), followed by MR contrast (0.0088%) and ultrasound contrast (0.0086%). The safety profile of Lumason™ has been documented in a large cohort including 23,188 adults, with no fatal event and only 29 (3 severe, 3 moderate, and 23 mild) adverse events. Further studies detail the safety profile of ultrasound contrast agents in children and have shown minor adverse events including nausea, tinnitus, lightheadedness, altered taste sensation. One documented severe reaction in a child documented symptoms of generalized pruritus, nausea, hypotension with tachycardia initially then bradycardia [6]. Management in this instance consisted of oxygen, intravenous epinephrine, and fluids (0.9% normal saline) with resolution of symptoms in two hours. Treatment of both minor, mild, and severe adverse reactions post Lumason™ administration are the same as that of CT or MRI contrast agents. In comparison to CT or MRI contrast agents, however, ultrasound contrast agents have proven to be much safer in children with only one serious adverse event over decades of its use to date (contrasting to approximately 15-20 adverse events per 2000 children if CT contrast agent were to be used). No serious adverse event has been reported in a neonate since its clinical use in this population. Animal studies on its toxicity profile also validate no fetal toxicity and the ultrasound contrast agent belongs to category B. However, a few serious adverse reactions in older patients have been reported, such as anaphylactoid/hypersensitivity reactions, arrhythmias and hypertensive episodes, commonly within 30 minutes of Lumason administration, some of them causing death.

Risks of the administration of the study drug are considered a minor increase above minimal risk, with no prospect of direct benefit for subjects. Adverse effects are not dose-dependent, thus risk is not increased by modifying the timing of interventions or increasing the number of contrast-agent injections.

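### Adverse-event monitoring during the scan is by intercom and watching, and no vital signs are planned around the injections, so causality ratings lack a planned baseline

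*Combined protocol and SAP*

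**What the plan says.** For the scan itself, Section 7 states that "all subjects will be monitored for adverse events during the procedure by direct communication through an intercom system and by visual observance". The same paragraph says that "we will follow all current safety standards for CEUS established by the FDA and ACR", without setting out what those standards require.

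Three other places add time windows:
- The procedures table in Section 3.1.1 schedules an acute adverse-event assessment less than 20 minutes after contrast.
- Section 6.1 has side effects monitored for 60 minutes after the last dose.
- Section 7.1 has adverse events monitored throughout the study.

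Section 7.3 counts any unfavourable sign as an adverse event, whether or not it is thought related. Each event must be recorded with its "nature, date and time of onset, determination of non-serious versus serious, intensity (mild, moderate, severe), duration, causality, and outcome of the event". Section 7.4.1 requires a relatedness term for each serious event.

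Section 8.3.2 describes one severe reaction in a child, which "documented symptoms of generalized pruritus, nausea, hypotension with tachycardia initially then bradycardia". It also says that a few serious reactions have been reported in older patients, including "arrhythmias and hypertensive episodes, commonly within 30 minutes of Lumason administration, some of them causing death".

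Eligibility under Section 3.3.1 includes "Patient has evidence of cardiovascular compromise, myocardial injury, acute kidney injury, and/or new-onset neurological symptoms" and "Patient 17 years of age or younger", with no lower age limit.

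**The concern.** The named method suits this population poorly. The synopsis places the scan at the bedside. Section 8.5 describes the children as critically ill and expects many to be unable to assent, and infants are eligible. An intercom helps only with a child who can speak. Watching may not show a fall in blood pressure or a change in rhythm, which are among the reactions that Section 8.3.2 lists.

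The same signs may also be present before contrast is given, because cardiovascular compromise and myocardial injury are qualifying conditions. Without a planned pre-injection value, an investigator who sees hypotension or tachycardia afterwards has no study record from which to judge whether it is new. Two things are at stake: complete capture of haemodynamic events, and the basis for the causality ratings. Relatedness is also one of the three conditions for prompt notification of the IRB in Section 7.5.

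**Working it through.** **Text check.** Every place where a measurement could be planned was read for heart rate, blood pressure, oxygen saturation, ECG or rhythm.

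| Section | What it plans | Vital signs? |
|---|---|---|
| 3.1.1, procedures table | Consent, eligibility, history, laboratory tests, contrast, scan, adverse-event assessment under 20 minutes | No |
| 4, study procedures | Dosing, organs scanned, low mechanical index | No |
| 4.1, study visit | Eligibility, consent, scan, COVID-19 policies | No |
| 4.4.1, chart variables | Symptoms, laboratory tests, medications, oxygen need, ventilation, complications | No |
| 6.1, study drug | 60 minutes of side-effect monitoring | No |
| 7 to 7.6, safety | Intercom and watching; recording, rating and reporting of events | No |

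The windows exist, but no measurement is attached to them.

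**How many events could be affected.** The plan gives no expected number of events, so there is no figure to reproduce. Inputs: n = 30 (Section 5.3); 29 adverse events in 23,188 adults, 3 of them severe, and an ultrasound-contrast rate of 0.0086% (all Section 8.3.2). Expected number = n × rate. Chance of none = (1 − rate)^n, treating children as independent.

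- Adult rate, any reaction: 29/23,188 = 0.00125. Expected 30 × 0.00125 = 0.04. Chance of none = (1 − 0.00125)^30 = 0.963.
- Ultrasound-contrast rate: 0.000086. Expected 30 × 0.000086 = 0.003. Chance of none = (1 − 0.000086)^30 = 0.997.
- Adult rate, severe reactions: 3/23,188 = 0.000129. Expected 30 × 0.000129 = 0.004. Chance of none = 0.996.

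The first line counts reactions of every kind, and 23 of the 29 were mild, so it probably overstates the haemodynamic events that vital signs could help with. In the other direction, these are not rates for children with cardiovascular compromise, and the document gives none.

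**The case against.** The strongest reply is that the values probably exist already. These are ill inpatients, the study team reviews their charts, and nothing stops the investigator from consulting charted vital signs when rating an event. That largely stands, and it limits the gain. What remains is that no section requires those readings, ties them to the injections or brings them into the study data.

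Second, the FDA and ACR standards may call for vital-sign checks. They may, but their content is not in the document, so this can be neither assumed nor excluded.

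Third, the child's reaction in Section 8.3.2 came with generalised itching and nausea and needed treatment with epinephrine, so staff would hardly have overlooked it. The arrhythmias and hypertensive episodes are reported as few and in older patients. Both points are fair. The list shows what kinds of reaction are known; it does not show that silent reactions are common in children.

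Fourth, a charted value in an unstable child, with no control group, separates contrast effect from illness only imperfectly. That also stands.

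A reader might infer that intercom and watching are the whole safety plan. They are not: Sections 3.1.1, 6.1 and 7.1 add assessments and windows. A reader might also infer that no child can report symptoms. Section 8.5 expects verbal assent from those aged seven or older who are able, and Section 4.3 rules out sedation and allows stopping for anxiety.

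**Conclusion.** The point holds as a modest improvement to descriptive safety data. The stated monitoring method fits the population poorly, no measurement is planned before or after contrast, and the required causality ratings therefore lack a planned baseline.

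The size is small: about 0.04 expected reactions of any kind in 30 children at the adult rate, and fewer at the other quoted rates. This assumes that those rates carry over to these children, which the document cannot confirm. The benefit lies mainly in judging the cause of any event that does occur.

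Three stronger readings are not supported:
- That reactions will be missed. An abnormal sign that staff notice is already recordable under Section 7.3, and ward monitoring may well be running.
- That the planned summary of event timing relative to the scan cannot be produced. Section 7.3 already requires the date and time of onset.
- That the study's main results are compromised. The endpoints in Sections 5.1 and 5.2 are perfusion measures and clinical outcomes from the chart, and do not depend on this monitoring.

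**What to change.** In Section 7, replace the intercom wording with bedside observation plus review of the inpatient's existing monitor. If the intercom is there for infection control, it can stay as an addition.

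In Section 4.4.1, add heart rate, blood pressure, oxygen saturation and any noted rhythm abnormality, taken from existing monitoring or charting:
- before the first injection;
- after each injection;
- at the end of the 60 minutes in Section 6.1, which extends beyond the 30 minutes mentioned in Section 8.3.2.

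Have the investigator review changes from the pre-injection value for adverse-event status and causality under Section 7.3.

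Cost: protocol wording and a little chart extraction. One injection gives 3 time points × 3 signs = 9 readings per child; two give 4 × 3 = 12. In 30 children that is 270 to 360 readings plus a rhythm note, with no new procedure. Downsides: the readings depend on charting close to the injections, brief changes can still be missed, and some recorded changes will reflect the illness.
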